Study of Regorafenib for Urothelial Cancer
Following Chemotherapy

Study Protocol & Statistical Analysis Plan

NCT02459119

February 19, 2020

[name]., Principal Investigator
University of Alabama at Birmingham
[name]

STUDY TITLE: A Multicenter, Non-Randomized, Phase II study of Regorafenib for Advanced Urothelial Cancer Following Prior Chemotherapy

Test drug(s): Regorafenib

[Study purpose:] Proof of concept

Clinical study phase: II

Version no.: 10 Date: 02-Dec-2018

Institution Study no.: **UAB1477 (Sponsor UAB, Funder Bayer)**

Principal Investigator: [name]
UAB Comprehensive Cancer Center
[name]
[name]
[contact]
[contact]
Email address: [contact]

Subinvestigators: [name]
UAB Department of Medicine
Division of Hematology/Oncology
[name]
[name]
[contact]
[contact]
E-mail address: [contact]

[name]
Wayne State University, Karmanos Cancer Institute
[name]
[name]
[contact]
[contact]
Email: [contact]

[name], PhD
Cleveland Clinic
[name]
[name]
[name]
[contact]
[contact]
Email: [contact]

Statistician: Name: [name]
Institution: UAB School of Medicine
Address: Ryals School of Public Health
City: Birmingham, State: AL
Country: USA
[contact]
[contact]
E-Mail: [contact]

The study will be conducted in compliance with the protocol, ICH-GCP and any applicable regulatory requirements.

Confidential

The information provided in this document is strictly confidential and is intended solely for the guidance of the clinical investigation. Reproduction or disclosure of this document - whether in part or in full - to parties not associated with the clinical investigation, or its use for any other purpose, without the prior written consent of the Principal Investigator is not permitted.

Throughout this document, symbols indicating proprietary names (®, TM) are not displayed. Hence, the appearance of product names without these symbols does not imply that these names are not protected.

Synopsis

[Title]	A Multicenter, Non-Randomized, Phase II study of Oral Regorafenib for Advanced Urothelial Cancer Following Prior Chemotherapy	
Clinical study phase	II	
Study objective(s)	Progression-free survival (PFS) at 6 months (PFS6)	
[Background treatment]	Platinum based chemotherapy	
Indication	Advanced urothelial or transitional cell carcinoma who have failed 1-3 previous treatments	
Diagnosis and main criteria for inclusion	Pathologically or cytologically confirmed locally advanced unresectable or metastatic invasive transitional cell carcinoma of the urothelium Progressive disease following 1-3 chemotherapy regimens	
Study design	Metastatic UC progressing after prior chemotherapy (N=35) → (15 slides of 10 µM sections, slides of 5 µM sections) 
 
  Regorafenib 120 mg po for 21 days of 28 days in cycle 1 increased to 160 mg po daily from cycle 2 or later if no Regorafenib- 
 
 Archival FFPE slides  Clinical and laboratory daily evaluation day 1 of each 28 day cycle  Radiologic evaluation every 8 weeks 
 
 
 
  Continue therapy until disease progression or intolerable toxicities 
 
  
 
	

Type of control	No control arm in this nonrandomized study
Number of subjects	35 patients; 4 sites
Plan for statistical analysis	A minimum of 32 evaluable subjects will be included in final analysis. Given that 5-10% of patients may be inevaluable, up to 35 patients may be enrolled. The alpha level of the design is 0.05 and the power is 0.8. Chi-square or Fisher's exact test will be employed to determine univariate association of biomarker status with PFS6 and objective response.

Table of contents

Title page.....	1
Synopsis.....	4
Table of contents	6
List of abbreviations.....	8
1. Introduction.....	10
1.1 Background.....	10
1.2 Rationale of the study	15
1.3 Regorafenib.....	16
1.3.1 Preclinical.....	16
1.3.2 Clinical experience.....	17
2. Study objectives.....	18
3. Investigator[s] and other study participants.....	18
4. Study design.....	19
5. Study population	19
5.1 Eligibility.....	19
5.1.1 Inclusion criteria.....	19
5.1.2 Exclusion criteria	20
5.1.3 Excluded therapies and medications, previous and concomitant.....	22
5.1.4 Selection of study population.....	22
5.2 Withdrawal of subjects from study	23
5.2.1 Withdrawal.....	23
5.2.2 Screen Failures/Dropouts	24
5.2.3 Replacement	24
6. Treatment[s].....	24
6.1 Treatments to be administered	24
6.2 Treatment assignment.....	24
6.2.1 Regorafenib.....	24
6.3 Blinding.....	24
6.3.1 Study Treatment.....	25
6.3.1.1 Dose Reduction Levels.....	25
6.3.1.2 Hypertension	29

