Since both PFS and OS are influenced by baseline clinical factors, interpretation of results of nonrandomized phase II trials needs to occur carefully. Indeed, survival has been shown to vary as a function of Eastern Cooperative Oncology Group (ECOG) Performance Status (PS), hemoglobin (Hb) and liver metastasis (LM) (15). Other factors may also impact on outcomes. A retrospective study of a large pooled prospective phase II trial dataset externally validated the independent impact of time from prior chemotherapy (TFPC), in addition to Hb, PS and LM, on PFS, although the independent impact of TFPC on OS could not be externally validated in the vinflunine phase III trial (16). However, the pooled phase II trial discovery dataset did demonstrate a strong independent impact of TFPC on OS. One major difference between the discovery dataset and validation datasets may possibly have hampered the external validation of an association of TFPC with OS: the inclusion of patients who had received prior peri-operative chemotherapy only in the discovery dataset, while patients in the validation dataset were required to have received prior chemotherapy for metastatic disease. A 4-variable nomogram has been constructed including Hb, PS, LM and TFPC to predict the activity of second-line therapy (i.e. PFS6) using historically used agents

(17). The comparison of observed vs. expected PFS6 may facilitate interpretation of PFS6 in nonrandomized trials, i.e. an observed PFS6 should be required to be at least similar and preferably superior to predicted PFS6. Notably, PFS6 has been demonstrated to be more robustly associated with OS, and performed better compared to response as an intermediate surrogate for OS (18). Finally, other variables such as number of prior lines of therapy, response to prior therapy, prior perioperative chemotherapy and site of primary (bladder vs. other) have not been identified to be independently prognostic after controlling for the above 4 major prognostic factors (19, 20).

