The angiopoietin ligands in the angiopoietin-tie1/2 signaling pathway have also been documented to be expressed in human subjects with UC (38). The expression of Ang-1 and -2 were assessed by IHC from 52 UCs of the bladder in this. Expression was detected in 18 samples (35%) for Ang-1 and in 23 samples (44%) for Ang-2. Ang-2 expression was also significantly correlated with histological grade, stage and poor prognosis. On multivariate analysis, positive Ang -2 expression was an independent negative predictor for survival ($P = 0.042$). Another study analyzed the expression of the mRNA of VEGF, Ang-1 and Ang-2 in 113 UCs (39). Multivariate analysis identified Ang-2 as an independent predictor of tumor recurrence and Tie2 expression as an independent favorable prognostic factor for both metastasis and disease-specific survival. These data show the strongest change in expression of VEGF and Ang-1 occurred in non-muscle invasive bladder cancer in comparison with normal bladder epithelium and the invasive tumor stages. One study analyzed the expression of mRNA for VEGF, Ang-1 and Ang-2 in 71 UCs (40). Low-stage superficial UC expressed VEGF and Ang-2 mRNA at a significantly higher level than high-stage muscle invasive carcinomas, and low-grade TCC at an insignificantly higher level than high-grade tumors. Conversely, Ang-1 mRNA was expressed at a significantly lower level in low-grade, low-stage compared to high-grade, high-stage UC. Thus, a significant drop of VEGF and Ang-2 mRNA expression coupled with higher Ang-1 in muscle-invasive cancer may represent a crucial event in progression.

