1.2 Rationale of the study

VEGF, FGF and TIE2 receptors appear to be key therapeutic targets in UC as described above. Although multiple trials are evaluating inhibitors of VEGF and FGF pathways,

inhibition of the TIE2 pathway has not been investigated in clinical trials. Given Regorafenib's broad kinase inhibition of all of these 3 critical angiogenic axis molecules, significant activity in UC may be anticipated. Thus, Regorafenib potently inhibits a broader range of angiogenesis-promoting molecules than Sunitinib, Sorafenib, Axitinib and Pazopanib. In particular, based on the impact of expression of TIE2, VEGF and FGF receptors on prognosis and preliminarily promising activity of TIE2, VEGFR and FGFR inhibition in UC in the aforementioned preclinical and clinical trials, the inhibition of all 3 of these pathways by Regorafenib receptors is a highly attractive property that may translate to more robust activity in a broader group of patients. Indeed, the inhibition of both VEGF and TIE2 targets together has been demonstrated to be more active than inhibiting only one of these targets in preclinical studies (56). Advanced UC is a malignancy with severe unmet needs and agents that provide increments in outcomes are necessary while a better understanding of basic biology of the disease accumulates.

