2.3 Exploratory objectives

- Association of tumor IHC for Tie2 and VEGFR2 with PFS
- Association of Gene expression in tumor tissue using Nanostring technology

3. Investigator[s] and other study participants

Principal Investigator

[name]
UAB Comprehensive Cancer Center
[name]
[name]
[contact]
[contact]
Email address: [contact]

Co-Investigators

[name]
[name]
[name]

[name], MD is a Professor in Department of Medicine, division of Hematology and Oncology at University of Alabama at Birmingham (UAB) and a Scientist at UAB Comprehensive Cancer Center (UABCCC). [name] is the director of urologic oncology at Wayne State University Karmanos Cancer Institute, and has extensively accrued in urothelial cancer trials and published multiple studies. [name], MD is an

[figure not shown]
Assistant Professor in the Department of Medicine, Division of Hematology and Oncology at UAB. He will see patients at Kirklin clinic along with [name]. [name] is a faculty urologic medical oncology physician with Cleveland Clinic where he is active with clinical trials and patient care.

4. Study design

This is a 3-center one-stage phase II trial conducted at the UAB Comprehensive Cancer Center (Birmingham, AL), Wayne State Karmanos Cancer Institute (Detroit, MI), and the Cleveland Clinic (Cleveland, OH). The trial will be managed by the Clinical Trial Network Monitoring Office (CTNMO) housed at the UAB Comprehensive Cancer Center. Progression free survival at 6 months is the primary end- point and the trial will enroll 35 patients. The eligible population includes patients with advanced urothelial cell carcinoma who have progressive disease after 1-3 prior chemotherapy regimens. Regorafenib is taken orally and is administered daily for the first 21 days of each 28 day cycle. The dose of Regorafenib is 120 mg once daily for the first cycle, which will be escalated to 160 mg once daily from the second cycle if no Regorafenib-related toxicities greater than grade 1 occur. Each 28 day cycle will be repeated until disease progression, intolerable toxicities, or patient decision with no limit on number of cycles allowed. Radiological evaluations are performed at each institution using RECIST 1.1 criteria every 2 cycles (8 weeks) or earlier if clinically indicated. Progression free-survival will be defined as the time to first occurrence of any of the following:

1. Clinical symptoms and signs of progression of disease,

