8.3 Statistical and analytical plans

The primary endpoint of the study is the rate of progression free survival (PFS) at 6 months (PFS6). Given the poor prognosis of this patient population and data from other studies of salvage therapy, a PFS6 of $\geq 20\%$ is felt to be important for this regimen, while a PFS6 $< 5\%$ is felt to be of poor interest. The trial also enrolls patients who progress within 6 months of last cycle of prior chemotherapy to enhance the interpretability of outcomes, since such patients are unlikely biologically to be progression-free for 6 more months without active therapy that favorably impacts on tumor biology to extend PFS. SAS version 9.3 was used to calculate power. The justification for the proposed sample size is based on an exact test for a binomial proportion with a one-sided significance level of 5%. With 32 evaluable subjects,

we will have approximately 80% power (79.6%) to reject the null hypothesis that PFS6 is < 5% in favor of PFS6 \geq 20%. Given that 5-10% of patients may be inevaluable, up to 35 patients may be enrolled. If five or more patients remain progression-free at 6 months, this regimen will be considered to be of significant interest.

Chi-square or Fisher's exact test will be employed to determine univariate association of biomarker status with PFS6 and objective response. Descriptive statistics including frequencies and proportions will be calculated to summarize safety and toxicity outcomes. Specifically, the number of adverse events (AE) and serious adverse events (SAE) will be tabulated and summarized. Point estimates and exact binomial (Clopper-Pearson) confidence intervals (CI) will be calculated to estimate the incidence of AEs and SAEs. The precision of these estimates, i.e., width of the confidence interval, will depend on the estimated incidence of each outcome. The table below gives the exact 95% confidence intervals for a range of incidences, assuming 32 evaluable subjects.

Number of subjects experiencing event	Estimated Incidence	95% Exact CI for Incidence		Width of CI
		Lower Limit	Upper Limit	
1	0.031	0.001	0.162	0.161
2	0.062	0.008	0.208	0.200
4	0.125	0.035	0.290	0.255
8	0.250	0.115	0.434	0.319
16	0.500	0.319	0.681	0.362

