A secondary objective is comparison of observed PFS6 vs. predicted PFS6 based on previously published nomogram. (17, 66). This internally and externally validated and calibrated nomogram uses PS (performance status), LM (liver metastasis), Hb (hemoglobin) and TFPC (time from prior chemotherapy) to predict PFS6 for an individual subject receiving historically used agents such as taxanes. We will use this nomogram to predict PFS6 for the patients in our study and compare the predicted values to the observed PFS6. The concordance index (c) will be calculated as a measure of the nomogram's discrimination ability. Predicted PFS will also be plotted against the observed PFS6 to provide a visual comparison.

9. Data handling and quality assurance

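### The exploratory biomarker analysis is univariate only; a test stratified by the nomogram-predicted PFS6 already being computed should be added beside it

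*Combined protocol and SAP*

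**What the plan says.** Section 2.3 lists as exploratory "Association of tumor IHC for Tie2 and VEGFR2 with PFS", together with gene expression on the Nanostring platform. The Synopsis (Plan for statistical analysis) and section 8.3 give one method for biomarkers: a chi-square or Fisher's "exact test will be employed to determine univariate association of biomarker status with PFS6 and objective response". No adjusted, stratified or multivariable biomarker analysis appears anywhere.

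Section 1.1.1 warns: "Since both PFS and OS are influenced by baseline clinical factors, interpretation of results of nonrandomized phase II trials needs to occur carefully". It names hemoglobin (Hb), performance status (PS), liver metastasis (LM) and time from prior chemotherapy (TFPC), and describes a nomogram that combines them to predict PFS6. Section 8.3 puts that tool to work: "We will use this nomogram to predict PFS6 for the patients in our study". Its only stated use is to compare predicted with observed PFS6 and to report a concordance index.

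On the markers, section 1.1.2 reports from a series of 113 tumors "Tie2 expression as an independent favorable prognostic factor for both metastasis and disease-specific survival". The synopsis states that there is no control arm. Section 7.2.1 says the tissue work may be performed, and section 7.2.2 obtains slides only if the primary endpoint is attained.

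**The concern.** A single-arm trial has no comparison that cancels out baseline risk. If marker-positive patients happen to have better PS, higher Hb, fewer liver metastases or longer time from prior chemotherapy, they will be progression-free at 6 months more often even when the marker has no bearing on outcome. A 2x2 table of marker against PFS6 then shows an association that belongs to the baseline factors. The bias is systematic: a larger sample or a multiplicity correction does not remove it.

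At stake is the reading of the exploratory result. A marker could be taken forward as linked to outcome on regorafenib when it only labels good-risk patients. The plan measures that risk and corrects for it in one secondary objective, but not here.

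**Working it through.** **The plan's own figure.** The only power figure in section 8.3 is for the primary test. With 32 evaluable patients and success defined as at least 5 progression-free:

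- power = P(X ≥ 5 | n = 32, p = 0.20) = 0.7956, against 79.6% stated;
- exact one-sided alpha = P(X ≥ 5 | n = 32, p = 0.05) = 0.0204.

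This reproduces and is untouched by the present point. No power or error rate is given for the biomarker tests.

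**Inputs for the biomarker check.** From section 8.3: 32 evaluable patients; PFS6 of 20% as the rate of interest; at least 5 successes for the regimen to be of interest. Assumed, because the documents give nothing: half the patients are good-risk, PFS6 by risk group, and the share of marker-positive patients in each group. The marker has no effect once risk is known, so the true odds ratio within each risk group is 1.

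**Formula.** Let g and p be PFS6 in good- and poor-risk patients, and a and b the marker-positive share in each. With equal groups:

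- PFS6 in marker-positive = (a·g + b·p) / (a + b)
- PFS6 in marker-negative = [(1−a)·g + (1−b)·p] / [(1−a) + (1−b)]

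Mild case, g/p = 30%/10%, a/b = 60%/30%:
- positive: (0.18 + 0.03)/0.90 = 23.3%; negative: (0.12 + 0.07)/1.10 = 17.3%
- odds ratio = (0.233/0.767)/(0.173/0.827) = 1.46

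Strong case, g/p = 40%/5%, a/b = 80%/20%:
- positive: (0.32 + 0.01)/1.00 = 33%; negative: (0.08 + 0.04)/1.00 = 12%
- odds ratio = (0.33/0.67)/(0.12/0.88) = 3.61

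**Rejection rates.** Simulated with 10,000 to 40,000 trials per row, two-sided 0.05. Fisher's test is compared with an exact conditional test stratified by risk group.

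| PFS6 good/poor | Marker+ good/poor | Odds ratio | Fisher, all trials | Fisher, ≥ 5 successes | Stratified exact |
|---|---|---|---|---|---|
| 20/20 or 35/5 | 50/50 | 1.00 | 2.4–2.5% | 2.7–2.8% | 2.7–3.0% |
| 30/10 | 60/30 | 1.46 | 4.3% | 4–5% | 2.3%* |
| 30/10 | 70/30 | 1.66 | 4.7% | 5.4% | 2.5% |
| 35/5 | 70/30 | 2.16 | 7.7% | 8.8% | 2.3% |
| 35/5 | 80/20 | 3.30 | 15.5% | 17.8% | 1.7% |
| 40/5 | 80/20 | 3.61 | 21.4% | 23.2% | 1.5%* |

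*All trials; the other stratified figures are given at least 5 successes.

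An even sharper assumption (38/2 with 80/20) gives an odds ratio of 4.39 and 26.0%. The baseline of 2% to 3% lies below 5% because Fisher's test is conservative at this size, so the first correlated rows use up slack and do not breach the nominal level.

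**What the data can carry.** At 20%, 32 × 0.20 = 6.4 successes are expected. With 5 to 7 successes, a model with the marker and four factors has 5/5 = 1.0 to 7/5 = 1.4 successes per term; marker plus one score has 5/2 = 2.5 to 7/2 = 3.5. With 5 successes and a 16/16 marker split, only a 5–0 division is significant (p = 0.043); 4–1 gives p = 0.33. A two-stratum exact test is feasible; a four-factor model is not.

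**The case against.** The strongest reply has four parts.

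1. *The work is exploratory.* It is conditional on the primary endpoint, promises only association, and is openly labeled univariate. No decision rule depends on it. This stands, and it limits the point to a cheap improvement.

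2. *The link to baseline risk is not shown.* A reader might infer that Tie2 and VEGFR2 are known to track risk, since section 1.2 argues "based on the impact of expression of TIE2, VEGF and FGF receptors on prognosis". The documents do not support that. Nothing ties either marker to Hb, PS, LM or TFPC. The VEGFR2 evidence contrasts muscle-invasive with non-muscle-invasive disease, a contrast absent among patients who all have metastatic or unresectable disease. The angiopoietin-2 findings concern a marker outside the planned IHC. The Tie2 finding concerns metastasis and disease-specific survival, not PFS6 after chemotherapy. Section 5.1.1 also requires the prior regimen within 6 months of registration, which narrows one of the four factors. So the bias is conditional.

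3. *Adjustment cannot isolate drug effect.* A reader might expect risk adjustment to show whether Tie2 predicts benefit from regorafenib. It cannot: if Tie2 is prognostic in its own right, no model separates that from a predictive effect in one arm. This stands, and calls for a stated limitation.

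4. *The nomogram is not established here.* It was built on second-line therapy with historical agents, while this trial enrolls after 1 to 3 regimens. This weighs against making an adjusted model the main analysis, or fixing the nomogram's slope through an offset. It weighs little against a two-group split shown as a companion, which uses only the ranking of patients.

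**Conclusion.** The point holds in a limited form. The biomarker analysis takes no account of baseline risk, although the protocol names the risk factors and computes a score from them. If a marker is correlated with that score, the univariate odds ratio is biased away from 1: about 1.5 to 3.6 under the assumptions shown, with Fisher's test rejecting in about 4% to 23% of trials. Under mild correlation the rate stays near 5%; without correlation it is 2% to 3%. Stratifying by risk returns it to roughly 1.5% to 3%.

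These figures rest on an assumed 50/50 risk split, assumed PFS6 by group, an assumed marker–risk correlation, and strata that capture risk fully. A real nomogram split would capture it only in part, so stratification would reduce the bias and need not remove it. The documents support neither a claim that the planned markers are confounded nor a claim that the univariate test must be replaced. The primary decision rule, its power and its alpha are unaffected.

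**What to change.** In section 8.3 and the synopsis:

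- Keep the univariate test. Add beside it one pre-specified exact test of each marker against PFS6, stratified at the median nomogram-predicted PFS6, with a rule for predictions tied at the median.
- Report both estimates with confidence intervals.
- Describe a marker as associated with PFS6 beyond baseline risk only if the stratified result supports it.
- State that the results are hypothesis-generating and that a single-arm trial cannot separate prognostic from predictive effects, including any prognostic effect of Tie2 itself.

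The cost is a few sentences and a few lines of code; the four inputs are already needed for the nomogram objective, so there are no new data or visits. Almost no power is lost when marker and risk are unrelated. When they are strongly correlated, the stratified test loses power with only about 5 to 7 successes, which is why it accompanies the univariate result and does not replace it. The change does not address multiplicity across the gene panel, which is a separate matter.
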